**Aim 3 Power Analysis.** Power analyses for cost-effectiveness analyses are based on assumptions regarding differences in cost and effect, standard deviations of cost and effect, the correlation of the difference in cost and effect, desired confidence and power levels, and the maximum willingness-to-pay value. Using a range of values for each of these factors, as well as the target sample size of 180 (60 per group), we estimated the power for the primary outcomes of these analyses: cost per QALY, cost per abstinent year, and cost per heavy drinking day averted. We estimate at least 80% power to be 95% confident that an intervention is a good value at the commonly cited lower-bound willingness-to-pay threshold of \$50,000 per QALY. Power for the cost-benefit analysis is more speculative. However, if the intervention cost is \$396 (SD=\$41) and there is a cost offset of \$1,000 from reductions in use of high-cost healthcare services, the net benefits would be \$604. To achieve 80% power, the standard deviation of the cost offset would have to be less than \$1,650. While difficult to forecast, it is not unreasonable to have a standard deviation less than 165% of the mean cost offset. Hence, we should have sufficient power for our cost-benefit analysis.

**Aim 4 Power Analysis.** For binary outcomes (e.g., submissions of EtG-negative samples), our trial will have at least 81% power to detect a 10% difference across the moderator (e.g., executive functioning) by group interactions. We will also maintain at least 80% power to detect a 13% difference in binary outcomes in our simple effects analysis or linear trend analysis to probe the interaction further. For continuous outcomes, our trial will have at least 80% power to detect a 30% mean reduction in continuous alcohol use measures (e.g., heavy drinking days) across the moderator (e.g., executive functioning) by group interactions. We will also have at least 82% power to detect a 44% mean reduction in continuous alcohol use measures (e.g., heavy drinking days) when conducting our simple effects analysis or linear trend analysis to probe the interaction further. Our planned analyses for Aim 4 provide sufficient power for nearly every scenario, even with a conservative estimate, because our missing data strategy will help to recover much of the lost power.]

## H. Timeline

Project Phase	Year 1	Year 2	Year 3	Year 4	Year 5
Start-up					
Recruitment					
Induction/Treatment period					
Follow-up					
Data analysis					
Dissemination of results					

## PROTECTION OF HUMAN SUBJECTS & RISKS TO THE SUBJECTS

### **A. Overview of Human Subjects Involvement, Sources of Materials, and Risks**

***A.1 Human Subjects Involvement and Characteristics.*** Participants will be 400 heavy drinkers diagnosed with moderate to severe alcohol use disorders (AUDs) and serious mental illness (SMI): schizophrenia, schizoaffective disorder, bipolar I or II, or recurrent major depressive disorder. All participants will be receiving treatment as usual at one of two partnering treatment agencies. Participants will be involved in the study for an 11-month period. Participants who meet inclusion/exclusion criteria and provide informed consent will take part in a study baseline interview and a 4-week induction period where reinforcement is delivered for providing urine samples 3 times a week. After the 4-week induction all participants who 1) attain an average EtG score of >499 ng/mL (suggesting frequent heavy drinking) AND 2) attend at least 1 study visit during the final week of the induction period will be randomized to treatment conditions. Based on pilot data and our screening procedures which will rule out light drinkers, we anticipate at least 60% of the 400 initially eligible participants will meet criteria for randomization (n=240). These participants will then be randomized to take part in one of the three contingency management (CM) interventions. All those who do not meet criteria for randomization will be referred to other AUD treatments available at our partnering agencies, and when necessary, other local providers.

During the 16-week treatment period, participants will submit urine samples 3 times a week to assess alcohol use. The 16-week treatment period will be followed by a 6-month follow-up period where outcomes will be assessed at 1-, 3-, and 6-months after the treatment phase. During the induction and treatment periods participants will complete other study outcome measures (e.g., self-report) on a monthly basis. Participants will be reimbursed for study participation at baseline (\$30), completion of the induction period (\$20), and at each of their monthly interviews (8 X \$20). The CM intervention duration is similar to previous studies.

It is expected that the demographics of participants in this study will reflect the overall gender and ethnic characteristics of the consumers currently receiving services at Community Psychiatric Clinic and Frontier Behavioral Health.

***A.2 Source of Study Materials.*** Research materials obtained from participants will include data on demographics, personal characteristics, psychological assessments, alcohol and drug use, urine specimens, and healthcare utilization. At the baseline interview each participant will sign a Health Insurance Portability and Accountability Act (HIPAA) form authorizing release of electronic medical records. Data and materials will be available only to authorized staff in a de-identified manner. All data with information concerning an individual participant, including urine samples and medical utilization data, will be marked with a unique code rather than the participant's name. The link between the code and the name will be stored on a password protected encrypted excel file that is only accessible by study staff. All medical utilization data will be transferred to investigators using an encrypted data transfer system. Direct identifiers will be removed from these data as soon as possible. To the extent possible, no information about a participant will be released to anyone without the participant's explicit written consent, except in the event of a medical emergency, when pertinent medical information will be given to medical personnel caring for the participant, or as required by law.

***A.3 Handling of Urine Samples.*** Urine is not considered a biohazard. However, over the last 8 years we have handled over 20,000 urine samples and have developed detailed procedures for the handling of urine. When handling urine all study staff will wear gloves, eye protection, and lab coats. They will follow appropriate disposal procedures for all urine and laboratory consumables. If a urine sample is observed to contain blood, our research staff will immediately place the urine sample in a biohazard bag and dispose of it at appropriate Washington State University biohazard receptacles located at each site.

***A.4 Potential Risks.*** The anticipated physical, psychological, social, and legal risks are minimal. However, as in all trials of this nature, possible outcomes include unauthorized disclosure of confidential information; discomfort or embarrassment related to urine collection or questionnaires dealing with personal habits, lifestyles, or drug or alcohol use; and possible unwanted encounters with friends or associates at the treatment center. If participants find any aspects of their involvement in the program psychologically or otherwise uncomfortable, they will be encouraged to discontinue participation and assisted in finding a more acceptable form of treatment. Alcohol withdrawal is another risk of study participation. Suicidal and homicidal thoughts and behaviors might also occur. Our team has extensive experience managing such behaviors. We describe how we will manage these risks in detail below.

### **B. Adequacy of Protection against Risks**

***B.1 Recruitment and Informed Consent.*** Clinic staff will give all potential participants a study brochure and a form asking if they would like to be contacted by study staff. Study staff will also describe the study at group treatment sessions and provide study contact information. Study staff will then either obtain contact

information for consumers who indicate interest in participation or will be contacted directly by interested consumers. Study recruitment materials will also be posted at locations that adults with co-occurring disorders are likely to frequent, such as transit centers and local hospitals. Study staff will contact potential participants to provide additional study information and screen for recent heavy drinking. Recruitment materials will be approved by the Washington State University Institutional Review Board. Initial interviews with potential participants and all subsequent contacts will be conducted in private offices at each study site. All information containing participant contact information will be stored in locked file cabinets in locked offices at each site.

Informed consent will be obtained in writing from all potential participants before research participation. During the initial interview, potential participants will be told about the study's purpose and all procedures involved. For those who decide to participate, study staff will administer the University of California, San Diego Brief Assessment for Capacity to Consent (UBACC), a brief screener of capacity to consent to research procedures designed for adults with psychiatric illness. Those who cannot demonstrate capacity to provide informed consent on this screener will be administered the MacArthur Competency Assessment Tool for Clinical Research (MacCAT-CR), a comprehensive, gold standard tool for assessing capacity to provide informed consent for adults with SMI. Only people with a demonstrated capacity to provide informed consent on these measures will be enrolled in the study. Staff will emphasize that there is no pressure to participate, that referral to alternative treatment will be provided if participants do not wish to continue in the study, and that potential participants are encouraged to speak to [name] or study staff about any concerns related to study participation. Issues of confidentiality will be discussed in detail. Interested adults will then read and sign the informed consent form in the presence of study staff, or study staff will read the form to them and witness their signature. Two forms will be signed, one for the participant to keep and another for study records. The latter form will be kept in a locked file separate from participant data. Participants who have questions about informed consent or any other aspect of the research at any time will be directed to [name]. Participants will complete a baseline interview within 2 weeks of signing the consent form. All research staff will receive extensive training in appropriate procedures to obtain informed consent, including administering measures of capacity to provide informed consent. They will conduct a mock consent interview for [name] to ascertain the adequacy of the consent process and ensure consistency in the process across participants. [name] has extensive experience in consenting adults with SMI through his previous studies.

**B.2 Protection Against Other Risks.** All study staff will be trained to be sensitive to issues surrounding confidentiality and other forms of participant risk. If at any time a participant expresses discomfort over any activity of the treatment program, staff will be told to discontinue the distressing activity and seek consultation to minimize risk. All data will be directly entered into a password-protected and encrypted RedCap database. The database will be hosted on a secure server at Washington State University and backed-up nightly. Study identification numbers will be the only identifier entered into the database. We will also request a Certificate of Confidentiality for this study from the NIAAA.

Potential participants will be thoroughly screened to eliminate candidates with disorders or conditions that are contraindicated, including high risk of alcohol withdrawal. Social risks from participation are expected to be minimal, since sensitive material is unlikely to be divulged. We will emphasize the confidential nature of all data collected in this study to potential participants. We will also explain thoroughly our safeguarding procedures. Participants who are judged by project investigators at any point to be a danger to self or others, or who are judged to be in grave danger due to continued alcohol or drug use or to medical or psychiatric problems, will be discontinued from the study but actively connected with appropriate treatment services. Details on this safety procedure will be included in the study consent form.

While our exclusion criteria are intended to prevent the participation of patients who are likely to experience dangerous alcohol withdrawal, we anticipate that withdrawal symptoms might occur, especially if the CM interventions are effective. Study staff will be trained to assess any and all symptoms of withdrawal and administer the SHOT, a brief and well validated measure of alcohol withdrawal symptoms, at each appointment. If withdrawal symptoms are observed, they will be immediately reported to [name]. He will consult with [name], as well as site medical personnel to decide how to best manage these symptoms. All sites are experienced and prepared to handle alcohol withdrawal. [name] has over 30 years of experience in the medical management of alcohol withdrawal. We have used this procedure in 3 RCTs of CM for alcohol use disorders and have had no cases of dangerous alcohol withdrawal. Any event that might affect participants' safety will be immediately reported to the [name], who will work with local healthcare providers to ensure participant safety.

[Through their research studies and clinical experience, Drs. [name] and [name] have extensive expertise managing suicidal and homicidal risk in adults with co-occurring disorders. [name], a licensed clinical psychologist, has 8 years of experience managing serious adverse events, including suicidal and violent thoughts and behavior in adults with co-occurring disorders. Through our studies, we have developed and

implemented protocols to manage suicide-risk and aggressive and violent behavior. Participants who report a suicidal attempt or self-harm behavior in the last thirty days and/or report repeated suicidal thoughts during the previous two weeks will be assessed for suicide risk by a treatment as usual clinician before they leave the clinic. The clinician will then determine the appropriate plan for managing suicide risk and refer participants to crisis or emergency services, if necessary. Study staff will also notify [name] when suicidal behavior or ideation is reported and the outcome of the clinician's assessment. Participants will be notified of this procedure at informed consent. All research staff will be trained in this procedure by [name], who has over 5 years of experience providing dialectical behavior therapy to patients with chronic suicidality and addiction. We have utilized this procedure in 3 of our CM RCTs and it is effective, with no-suicidal behaviors occurring after our procedure was implemented.

Consistent with the literature, we have observed extremely low rates of homicidal ideation or violent behavior in our studies of adults with SMI. During the thousands of visits with over 300 participants, 2 participants have made verbal threats or engaged in violent behavior (shoving a staff member). We have managed each of these situations in close collaboration with treatment as usual clinicians. Because our research takes place in community clinics, research staff will be trained in and comply with all clinic safety procedures. All threats of violence will be taken seriously by study staff who will follow clinic and study procedures, staff these cases with the Drs. [name] and [name], and call 911 if a potentially life threatening situation occurs. Additionally, study staff will follow all laws pertaining to mandated reporting of child or elder abuse. All of these events will also be reported to the study's Data Safety Monitoring Board, the National Institutes of Health, and the Institutional Review Board, as described in the Data Safety Monitoring Plan.]

**B.3 Adverse Events.** We have developed project stopping rules to protect the safety of study participants. In the case of a Serious Adverse Event (as defined by the FDA and the Washington State University Institutional Review Board), the study will be stopped and no further enrollment will take place until an investigation of the event has been conducted by [name] , the Co-Investigators, the Data Safety Monitoring Board, and Partnering Agency Leadership. A determination of the association of the adverse event with the study intervention will be made and appropriate modification of the protocol will be executed if an association is suspected. If protocol modifications to ensure the safety of future study participants cannot be executed, the study will be terminated. Serious Adverse Events will be reported to the Washington State University Institutional Review Board within 24 hours and to the appropriate program officer of the National Institutes of Health within 48 hours. [name] must decide whether the event should be classified as serious or not by using standard FDA guidelines for Serious Adverse Events. Non-serious events will be reported to the Data Safety Monitoring Board quarterly and to the program official and Institutional Review Board annually.

**B.4 Data Safety Monitoring Plan and Board.** This Human Subjects Research meets the National Institutes of Health definition of a Phase II clinical trial. This clinical trial requires registration in ClinicalTrials.gov. Because this is a multi-site trial an appropriate Data Safety Monitoring Board and Plan has been developed and is described in the Data Safety Monitoring Plan section of the application.

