## F. Data Collection and Measures

**4.F.1 Schedule.** Data collection will occur during the study period (weeks 1-20, including baseline assessment, induction, and treatment) and the follow-up period (weeks 21-47) as shown in **Table 4**. Baseline data collection will take ~120 minutes and include urine tests, self-reported data, and cognitive tests. Participants will provide urine samples every Monday, Wednesday, and Friday during the study period. At each visit, they will complete brief self-report questionnaires on alcohol use. Weeks 4, 8, 12, 16, and 20 will include 45-minute data collection visits to assess other outcomes. During follow-up, participants will be scheduled for 45-minute visits at weeks 25, 33, and 47. They will receive a \$30 gift card for completing the baseline interview and a \$20 gift card for completing each interview in weeks 4, 8, 12, 16, 20, 25, 33, and 47.

**Table 4.** Data collection schedule

Measure	Baseline Wk 0	Induction Wk 1-4	Treatment Wk 5-20	Follow-up Wk 25, 33, 47
Eligibility Criteria				
DSM-5 inclusion/exclusion diagnosis (interview)	✓			
Consumer at participating agency (self-report)	✓			
Age (self-report)	✓			
Current heavy drinking (self-report)	✓			
Health and risk factor exclusions (self-report/observation)	✓			
Primary Outcome				
Alcohol use (ethyl glucuronide)	✓	3x / Wk	3x / Wk	Every visit
Other Secondary Outcomes				
Any/Heavy drinking: ATLFB (self-report)	✓	3x / Wk	3x / Wk	Every visit
Recent heavy drinking (ethyl glucuronide)	✓	3x / Wk	3x / Wk	Every visit
Alcohol cravings (self-report)	✓	Weekly	Weekly	Every visit
Alcohol/ drug severity: ASI-Lite (self-report)	✓	Wk 4	Wk 8,12, 16, 20	Every visit
Drug use (biochemical)	✓	3x / Wk	3x / Wk	Every visit
Cigarette Timeline FollowBack (self-report)	✓	Wk 4	Wk 8,12, 16, 20	Every visit
Nicotine dependence: Fagerstrom (self-report)	✓	Wk 4	Wk 8,12, 16, 20	Every visit
HIV risk behavior (self-report)	✓	Wk 4	Wk 8,12, 16, 20	Every visit
Psychiatric symptoms: PANSS (interviewer rating)	✓	Wk 4	Wk 8,12, 16, 20	Every visit
Economic Measures				
Drug Abuse Treatment Cost Analysis Program tool				Wk 47
Healthcare use by patient medical records	Past 12 mo	Throughout	Throughout	Throughout
Non-Study Resources Form (self-report)	✓	Wk 4	Wk 8,12, 16, 20	Every visit
Quality-Adjusted Life-Years: EQ-5D (self-report)	✓	Wk 4	Wk 8,12, 16, 20	Every visit
ANA Moderators				
Negative emotionality: NIH Toolbox (self-report)	✓	Weekly		

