Executive functioning: NIH Toolbox/MCQ (cognitive tests/self-report)	✓			
Alcohol incentive salience (self-report/cognitive tests)	✓			
Adverse Events				
Alcohol withdrawal: SHOT (interviewer rating)	✓	3x / Wk	3x / Wk	Every visit
Participant safety (self-report/observation)	✓	3x / Wk	3x / Wk	Every visit

**4.F.2 Measures Overview.** Baseline data will include assessment of eligibility criteria and measures for Aims 1-4. Our primary outcome (Aim 1) is biochemically confirmed alcohol abstinence, measured 3 times per week during the final 12 weeks of the treatment period (weeks 9-20) and 3 times total during the 6-month follow-up period. Aim 2 outcomes will be collected in a similar fashion. Cost data will be collected for 12 months before and after randomization. Aim 3 outcomes consist primarily of self-reported use of non-study

healthcare resources, QALYs, days of alcohol abstinence, and heavy drinking days averted. We will collect data on each ANA domain to test for predictors of alcohol abstinence during CM interventions.

**4.F.3 Eligibility Criteria.** Age and frequency of recent drinking will be assessed by phone screening. The Structured Clinical Interview for DSM-5 (SCID-5) interview, clinical trials version, will be administered to assess diagnostic inclusion (SMI, AUDs) and exclusion criteria. Competency to provide informed consent will be assessed as described in Section 4.C.2.

**4.F.4 Primary Outcome.** Our primary outcome will be alcohol abstinence during the last 3 months of treatment and the 6-month follow-up period. At each study visit, urine samples will be collected and analyzed onsite for EtG by using the [commercially available Diagnostic Reagents Incorporated EtG immunoassay on an Indiko Bench Top Analyzer (ThermoFischer Scientific, Freemont, CA).] We will use the assay to create a binary indicator of alcohol use defined by EtG < 100 ng/mL. That threshold was used in our first funding period and in our ongoing CM trials. While it is not associated with false positives due to non-beverage alcohol exposure, we will ask participants to abstain from using all alcohol-containing products, like hand sanitizer.

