**Aims 1 and 2.** Recent alcohol use will be documented by using urine test results (binary outcome: EtG < 100 ng/mL or EtG > 100 ng/mL) and analyzed by using generalized estimating equations (GEE), generalized regression, and Cox proportional hazard regression techniques. Other outcome measures will be derived from recent alcohol use, such as 1) alcohol use (yes/no) over time; 2) longest duration of abstinence; 3) total number of periods of alcohol abstinence; 4) time to first alcohol abstinence; and 5) time to relapse after a specified period of alcohol abstinence. These outcomes will be examined across CM condition, time, and the CM condition-by-time interaction to determine whether one condition is superior to the others in promoting discontinuation of alcohol use. Additional analyses will be conducted by defining alcohol use in various clinically descriptive ways, such as the mean number of heavy drinking days or heavy drinking months across groups. Group comparisons of other Aim 2 outcomes will be assessed and evaluated in a similar fashion (e.g., longest duration of drug abstinence, mean HIV risk score).

Analyses will be conducted on the intent-to-treat sample (n=240). This is a conservative approach aimed at avoiding overestimation of the treatment effect. It includes all participants who were randomly assigned to treatment conditions, regardless of treatment completion. GEE models will be used to evaluate the differential change in primary and secondary outcomes by study condition over the 12-month study period (1 month before the baseline interview plus the 1-month induction, 4-month treatment, and 6-month follow-up periods), and whether condition interacts with change over time. This approach allows us to characterize between-group differences in longitudinal outcomes. We hypothesize that the modified interventions (High-Magnitude CM and Shaping CM) will lead to higher rates of alcohol abstinence than the Usual CM intervention. If the condition-by-time interaction variable is significant, we will conduct planned comparisons to examine the hypothesized pattern for each outcome. Such an approach will allow us to test this set of hypotheses with specificity. We will also conduct a direct comparison of the High-Magnitude CM group and the Shaping CM group.

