appropriate reference case. All values will be adjusted for inflation. Since no follow-up measurements will be taken beyond 12 months following baseline, discounting for time preference will not be required. Given the differences in mechanisms to generate data, separate multivariable generalized-linear models (GLMs) will be estimated to predict the mean value of each resource category at each time point. GLMs permit us to choose the most appropriate mean and variance functions according to fit with the data. A multivariable GLM will also be used to predict health-related quality of life preference weights for each participant at each time point. QALYs gained by the intervention will then be estimated by using the area under the curve. The method of recycled predictions will be used to obtain the final predicted mean values for each study group and resource, which will then be summed and tested according to the relevant perspective. To account for sampling uncertainty in point estimates, both the p-values and standard errors, as well as the confidence intervals for the ICER, will be estimated by using nonparametric bootstrapping techniques within the multivariable framework. Parametric methods based on parameters obtained from bootstrapping will be used to estimate acceptability curves, which illustrate the probability that the intervention is a good value for different willingness-to-pay thresholds (e.g., cost-per-QALY). Sensitivity analyses will be performed to account for uncertain precision in assumptions and parameter estimates applied in the analysis.

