**[Aim 4.]** We will examine whether the ANA moderators (executive functioning, negative emotionality, alcohol-related incentive salience) interact with CM, and if so, with which CM condition. This will help us determine whether a given moderator significantly modified the impact of CM on alcohol abstinence. First, we will create an interaction term of CM condition by the moderator in question and examine whether the interaction is significant. Second, if the interaction is significant, we will examine whether the outcome varies within each CM condition across 3 categories of the moderator in question: 1) Mean  $\pm 1$  standard deviation, 2)  $> 1$  standard deviation, and 3)  $< 1$  standard deviation. This will be accomplished by conducting a planned linear trend analysis or simple effects analysis for each CM condition, since we hypothesize that, for example, more executive dysfunction will produce worse treatment outcomes. Although we anticipate that this association will hold true for each condition, we also hypothesize that the effect will be more pronounced in the Usual CM condition. If appropriate for a clearer clinical interpretation, we will use centering (i.e., subtracting the mean from all participant values on the measure) on the moderator being examined, which is consistent with current expert recommendations.

**Missing Data.** We have developed extensive tracking procedures to reduce missing data, which will be handled in a manner consistent with current expert recommendations. We will use maximum likelihood or multiple imputation and extensive sensitivity analyses, including “missing not at random” approaches, to examine the robustness of treatment effects under varying assumptions. These approaches are preferable to other data imputation approaches, such as mean imputation.

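### The B.2 safety rule ends study participation, not only CM, and no supplied section keeps the removed participant's later outcome assessments

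*Combined protocol and SAP*

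**What the plan says.** **The rule.** Protection of Human Subjects, B.2, applies at any point in the trial. Participants whom the investigators judge a danger to self or others, or "in grave danger due to continued alcohol or drug use or to medical or psychiatric problems, will be discontinued from the study", are to be linked to treatment services. No further assessment is mentioned. B.2 adds: "Details on this safety procedure will be included in the study consent form".

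**The outcome schedule.** Section 4.F.1 states: "During follow-up, participants will be scheduled for 45-minute visits at weeks 25, 33, and 47". Section 4.F.2 defines the primary outcome as EtG-confirmed abstinence, sampled three times a week in weeks 9-20 "and 3 times total during the 6-month follow-up period". Table 4 places the EQ-5D at baseline, at weeks 4, 8, 12, 16 and 20, and at each follow-up visit.

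**The analysis.** On the intent-to-treat sample, 4.G.2 says: "It includes all participants who were randomly assigned to treatment conditions, regardless of treatment completion". For missing data it says: "We will use maximum likelihood or multiple imputation and extensive sensitivity analyses", and these include missing-not-at-random approaches. Aim 3 takes the QALY as its main effectiveness measure: "QALYs gained by the intervention will then be estimated by using the area under the curve".

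**Record data.** Under A.2, at the baseline interview "each participant will sign a Health Insurance Portability and Accountability Act (HIPAA) form authorizing release of electronic medical records".

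**The concern.** B.2 makes one decision where two are needed: whether the intervention should stop, and whether measurement should stop. A clinician may have good reason to end CM for someone in danger. That reason does not always extend to a urine test and a short interview some weeks later.

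One trigger is grave danger from continued alcohol or drug use, which is related to the primary outcome. Values lost this way may therefore be informative. Anyone removed before week 25 would have no EtG or EQ-5D result at weeks 25, 33 or 47, and anyone removed during treatment would also lose the remaining treatment-period samples. The likelihood, imputation and sensitivity methods in 4.G.2 can model such values but cannot recover them once the visit window has passed.

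The economic analysis is the more exposed part. Record-based costs would probably continue for a removed participant, because release is authorized at baseline. Most of that person's utility curve would be imputed, in someone whose health state is likely to be unusual.

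**Working it through.** **1. Does other text restore the visits?**

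- Section 4.B (Overview) and 4.F.1 schedule follow-up for randomized participants in general. Neither mentions people removed under B.2.
- The intent-to-treat statement in 4.G.2 defines who is analysed. It does not order visits after someone leaves the study.
- The tracking procedures in 4.G.2 (Missing Data) are general.
- B.2 uses narrower wording elsewhere: when a participant is uncomfortable, staff stop the activity concerned. The safety rule stops the study.
- The suicide-risk procedure later in B.2 sends the participant to a clinician and does not mention removal. Staff thus have two procedures for overlapping events, and neither says when visits continue.

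No supplied section keeps the visits.

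**2. The plan's own attrition figure.** From 4.G.3: 240 × (1 − 0.25) = 180, or 60 per group. This reproduces. The plan does not say whether safety removals are inside the 25%. If they are, the sample size is unaffected.

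**3. Share of the primary outcome.** 12 weeks × 3 + 3 = 39 samples. Follow-up share: 3/39 = 8%.

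**4. Share of one person's QALY curve.** Trapezoid weights in weeks, from the EQ-5D times in Table 4:

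| Week | 4 | 8 | 12 | 16 | 20 | 25 | 33 | 47 |
|---|---|---|---|---|---|---|---|---|
| Weight | 2 | 4 | 4 | 4 | 4.5 | 6.5 | 11 | 7 |

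The sum is 43. Weeks 25, 33 and 47 carry 6.5 + 11 + 7 = 24.5, and 24.5/43 = 57%. Counted from week 0 the share is 24.5/47 = 52%. This is time-weight within the curve of one participant removed before week 25.

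**5. Illustrative size.** The documents give no removal rate, so every input here is an assumption: a removal gap between arms of 1 to 5 percentage points, 5% to 20% abstinence imputed for removed participants, and all of them in fact drinking. With 240/3 = 80 per arm, a 1-point gap is 0.8 of a person and a 5-point gap is 4 people.

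- Follow-up visits, shift = gap × imputed abstinence: 0.01 × 0.05 = 0.05 points, to 0.05 × 0.20 = 1.0 point.
- With half of these visits attended (× 0.5): 0.025 to 0.5 points. With three quarters attended (× 0.25): 0.0125 to 0.25 points.
- Pooled over 39 equally weighted samples, removal before week 9: 0.05 to 1.0 points. If all three follow-up visits are kept (× 36/39): 0.046 to 0.92.
- Pooled, removal after 18 samples (× 21/39): 0.027 to 0.54. With the three visits kept (× 18/39): 0.023 to 0.46.
- Reverse case, 30% of removed participants truly abstinent (for example as inpatients) and 5% imputed: 0.05 × (0.30 − 0.05) = 1.25 points in the other direction.
- QALY, with imputed utility wrong by 0.05 to 0.20: 0.01 × 0.05 × 24.5/52 = 0.0002, to 0.05 × 0.20 × 24.5/52 = 0.0047 per person. At the $50,000 threshold in 4.G.3 that is $12 to $236.

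For comparison, 4.G.3 aims to detect differences of 7 to 8 points, and Table 3 puts expected payout at $1,000 for High-Magnitude CM and $500 for Usual CM.

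**The case against.** The strongest objection is that the answer may lie in documents not seen here. B.2 sends the detail to the consent form, and the human-subjects section sends safety reporting to a Data Safety Monitoring Plan; neither was supplied. The Overview also says, without exception, that randomized participants complete follow-up. This stands as a limit. The point is that no supplied section keeps the visits, not that the trial has no such provision. The general sentence does not displace a specific rule that names the study as what is discontinued.

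Second, removal looks rare. B.2 reports no dangerous withdrawal in three earlier trials, no suicidal behavior once the current procedure was in place, and threats or violence from 2 of more than 300 participants (under 0.7%). Nothing suggests that removal would differ by arm. This stands too and points to the low end of the ranges, although no rate is given for the alcohol, drug, medical or psychiatric triggers.

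Third, ending contact can be right: it may protect staff, and a participant in crisis may be unable to agree to visits. That is why the change must be conditional on safety and agreement, and why it will recover only some visits.

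Fourth, 4.G.2 already plans imputation and missing-not-at-random analyses. That answers how missing values would be treated, but not whether they need be missing. Which sensitivity scenarios to run is the trial team's choice.

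**Conclusion.** The point holds as a low-cost improvement. B.2 as written turns a safety decision into the loss of outcome data, and one trigger is related to the outcome. The effect is expected to be small. It cannot be quantified, because the plan gives no removal rate and the figures in step 5 rest wholly on assumed inputs. Its direction is also unknown.

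A reader might infer more than the documents support:

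- *That continued drinking alone removes a participant.* It does not; the rule requires a judgment of grave danger.
- *That the intent-to-treat analysis is contradicted.* It is not; removed participants stay in the analysis set and a missing-data method is specified.
- *That the primary result is at risk.* The follow-up visits are 8% of the samples, and even the assumed extremes fall well below 7 to 8 points. Keeping the three visits would change the pooled shift only slightly.
- *That 57% of the QALY information is lost.* That figure is the share of time-weight for one removed participant, not a trial-level effect.

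**What to change.** Leave the clinical decision as it is. Change B.2 to say that CM and any unsafe procedures stop, while the remaining scheduled assessments, at least those at weeks 25, 33 and 47, continue where safe and where the participant agrees, and that collection of authorized record data also continues. Use matching wording in the consent form; if it already says this, repeat the sentence in B.2. Report the number removed under the rule by arm and reason.

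The cost is one sentence in B.2, matching consent text and one line in the participant-flow report. The downside is minor follow-up effort, with uncertain attendance, for a few participants already referred elsewhere. The wording should be settled before any removals occur.
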